#### 10.1.2.4 IBS Symptom Severity Score

The IBS Symptom Severity Score (IBS-SSS) measures the severity of IBS symptoms through a series of questions and visual analog scales (VAS). Part 1 of the IBS-SSS generates the severity score, as described in Appendix 4 of the protocol. Part 2 consists of Bowel Habit and Site of Pain sub-sections that are not converted to a score.

#### 10.1.2.5 Hospital Anxiety and Depression Scale

The Hospital Anxiety and Depression Scale (HADS) is commonly used by doctors to determine the levels of anxiety and depression that a person is experiencing. The scale consists of a series of statements about which subjects must respond with their feelings. Each statement has a set of ordinal responses with scores 0 to 3 or 3 to 0.

Some statements correspond with anxiety and some with depression, as given in the table below.

| Statement   | Characteristic |
|---|----------------|
| I feel tense or wound up  | Anxiety        |
| I get a sort of anxious feeling like butterflies in the stomach             | Anxiety        |
| I get a sort of frightened feeling as if something awful is about to happen | Anxiety        |
| I feel restless as if I have to be on the move                              | Anxiety        |
| Worrying thoughts go through my mind  | Anxiety        |
| I get sudden feelings of panic  | Anxiety        |
| I can sit at ease and feel relaxed  | Anxiety        |
| I feel as if I am slowed down   | Depression     |
| I enjoy the things I used to enjoy  | Depression     |
| I have lost interest in my appearance                                       | Depression     |
| I can laugh and see the funny side of things                                | Depression     |
| I look forward with enjoyment to things                                     | Depression     |
| I feel cheerful   | Depression     |
| I can enjoy a good book, radio or television program                        | Depression     |

[figure not shown]
An Anxiety and a Depression Total Score ranging from 0 to 21 each are derived by summing the individual scores under each category. The Total Scores are interpreted as:

0-7 = Normal,  
 8-10 = Borderline abnormal (borderline case)  
 11-21 = Abnormal (case)

### 10.1.3 Exploratory Efficacy Endpoints

CCI

### 10.2 Baseline Values for Efficacy Assessments

For the daily assessments collected on the eCOA device, baseline values will be derived from the 7 consecutive days assessed preceding the Baseline (Day 1) visit used to assess eligibility. The baseline value will be considered missing if less than 4 of the 7 days have an assessment.

- Abdominal Pain Intensity (1-10)

- Stool Consistency (day with at least one bowel movement Type 6 or 7)
- Stool Frequency

The baseline value for each of these assessments will be calculated by summing the daily result over the 7-day period and dividing by the number of days with an assessment. The Stool Consistency baseline proportions will be multiplied by 100 to convert to a percentage.

Baseline for the other efficacy assessments is defined as the last non-missing value recorded on or before the Baseline (Day 1) visit.

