5.1 Inclusion Criteria

All subjects must meet all the following inclusion criteria:

- 1. Written consent on an Institutional Review Board (IRB)/ Independent Ethics Committee (IEC) approved ICF before any study specific evaluation
- 2. Males and Females between 18 and 70 years of age
- 3. Body Mass Index (BMI): 18-39 kg/m²
- 4. Having IBS-C or IBS-D as defined by Rome IV, including Subtype Classification as defined per Table 2

Recurrent abdominal pain on average, at least 1 day/week in the last 3 months associated with two or more of the following criteria:

• Related to defecation

- Associated with a change in frequency of stool
- Associated with a change in form (appearance) of stool

The above criteria must be met for the last 3 months with symptom onset at least 6 months prior to diagnosis.

IBS-C and IBS-D subtypes will be further classified as follows:

Table 3:

IBS-C	IBS-D
□ Abdominal Pain Intensity: weekly average of worst daily (in past 24 hours) abdominal pain score of > 3.0 on a 0 to 10-point scale	\Box Abdominal Pain Intensity: weekly average of worst daily (in past 24 hours) abdominal pain score of > 3.0 on a 0 to 10-point scale
	And
And	
□ Stool Frequency: more than 25% of bowel movements with a consistency of Type 1 or Type 2 Bristol stool chart and less than 25% of bowel movements with Bristol stool form Type 6 or Type 7. Subject must have fewer than 3 CSBMs ¹ within a one week period (7 days)	□ Stool Consistency: more than 25% of bowel movements with a consistency of Type 6 or Type 7 Bristol stool chart and less than 25% of bowel movements with Bristol stool form Type 1 or Type 2. Subjects must have at least one Type 6 or Type 7 bowel movements on at least four days within a one week period (7 days).

*Stool types based on Bristol Stool Chart; Hard stools -Type 1 and 2; Soft stools – Type 6 and 7 (see Appendix 3). Source: (https://irritablebowelsyndrome.net/clinical/new-rome-iv-diagnostic-criteria/) (see Appendix 6) ¹ CSBM defined as a bowel movement that is both complete and spontaneous. Bowel movements where laxative use is recorded in the concomitant medication questions in a 24 hour period, by IBS-C subjects will not be counted as CSBMs when subtyping for randomisation.

- Have a moderate or severe IBS symptom severity score ; ≥175 at the screening visit as defined by IBS-SSS. A tolerance of -10% (≥ an IBS-SSS score of 157.5) will be allowable at the Baseline (Visit 1).
- 5.2 Exclusion Criteria

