Subjects will be asked to complete a quality of life questionnaire consisting of 34 questions with a five-point response. The individual responses to the 34 items are summed and averaged for a total score and then transformed to a 0-100 scale for ease of interpretation with higher scores indicating better IBS specific quality of life. Once subjects are randomised they will be asked to record their score on their smartphone at each clinic visit or within 24hrs prior to the Clinic Visit.

Hospital Anxiety and Depression Score (HADS) (Appendix 2)

Subjects will be asked to complete HADS which is a 14-item scale that generates ordinal data. Seven of the items relate to anxiety and 7 relate to depression. Each item is scored from 0-3 so a subject can score 0 to 21 for either anxiety or depression. Once subjects are randomised they will be asked to complete this questionnaire on their smartphone at each clinic visit or within 24hrs prior to the Clinic Visit.

Bristol Stool Chart

Subjects will be asked to record stool frequency and consistency. Stool types will be based on the Bristol Stool Chart (Appendix 3). This data will be recorded daily for a 7-day period up to Baseline (Visit 1) to allow Subject to be classified into Cohorts of IBS sub-types. Once subjects are randomised they will be asked to record their stool frequency daily up to 10 bowel movements per day and score each stool type on their smartphone. No bowel movements in any given day will also be recorded.

Stool frequency will be defined as a sum of weekly CSBMs. Stool frequency will be recorded using the following question: "How many times did you open your bowels during the past 24 hours? If you have not had any bowel movements today, please enter 0." Subjects will be reminded to rate all of their bowel movements in the Bristol Stool Chart before answering the question. CSBMs will be determined by absence of laxative use recorded in concomitant medication questions for the same 24 hour period.

IBS Symptom Severity Score (SSS) (Appendix 4)

Subjects will be asked to complete a questionnaire on severity of abdominal distension, severity of abdominal pain, frequency of abdominal pain, dissatisfaction with bowel habits, and interference of IBS symptoms with daily life. A score ranging from 0 (no symptoms) to 500 (maximum severity) can be achieved as mild (74-174), moderate (175-299) or severe (>300) IBS symptoms.

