#### 10.1.1 Primary Efficacy Endpoint

The primary efficacy endpoint is whether the subject is an overall responder. The definition of an overall responder is IBS subtype specific and consists of two components.

For both IBS subtypes, the first component of overall response is the weekly average of Abdominal Pain Intensity (0-10, 0=none, 10=worst possible pain) over the past 24 hours. Improvement for the week is defined as a decrease of at least 30% compared with baseline.

For the IBS-C subtype, the second component of overall response is the stool frequency per week. Improvement is defined as an increase of 1 or more complete spontaneous bowel movements (CSBMs) per week compared with baseline. The number of bowel movements is recorded once per day in the eCOA device, including zeroes.

For the IBS-D subtype, the second component of overall response is the proportion of days per week with at least one stool with a consistency of Type 6 or 7 on the Bristol Stool Chart. Improvement is defined as a decrease in the proportion of at least 50% compared with the proportion during the 7-day period before baseline used to determine eligibility. Stool consistency is recorded for each bowel movement in the eCOA device, so more than one entry per day may exist. The daily result should be reduced to whether a Type 6 or Type 7 was included on that date.

A subject will be considered a responder only during weeks for which both components indicate improvement. Subjects must have at least 4 evaluable weeks of data as defined in [Section 10.4](#) for each of the instruments used to determine response. Subjects with less than 4 evaluable weeks of assessments available during the treatment period will be considered as non-responders for overall response.

Subjects who have at least 7 evaluable weeks of data and have reported an improvement in their weekly symptoms for  $\geq 50\%$  of the treatment period will be considered overall responders. Subjects who have 4, 5, or 6 evaluable weeks of data must show improvement for  $\geq 60\%$  of the treatment period to be deemed overall responders.

The days for each week will be taken as calendar days from the Day 1 date (randomisation date).

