The denominators for the weekly average of Abdominal Pain Intensity, the stool frequency, and the proportion of days per week with at least one Type 6 or 7 will be the number of days with an assessment during the week. The stool frequency will be multiplied by 7 to convert to a stools per week figure. The stool consistency will be multiplied by 100 to convert to a percentage.

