### 10.4 Handling of Dropouts or Missing Data

In general, missing data will not be imputed. Summary data for observed cases only will be presented.

For weekly assessments derived from daily eCOA data, the weekly values will be considered missing if there are less than 4 days with data assessed within a week.

For the primary endpoint, overall response, subjects must have at least 4 evaluable weeks of data. An evaluable week is one in which there are at least four 24-hour daily records of abdominal pain score, number of CSBMs, and Bristol stool chart. If number of CSBMs for a date is 0, then Bristol stool chart data is expected to be missing. The day will still count towards the 4-day minimum. Subjects with less than 4 evaluable weeks of data will be considered non-responders.

Mixed model repeated measures (MMRM), which provide valid parameter estimates even with some values missing, will be used to analyze continuous assessments taken over time.

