#### 11.3.2 Stool Frequency/Consistency

The mean derived weekly stool frequencies, mean changes from baseline, and mean percent changes from baseline will be summarized by IBS subtype, treatment group, and week. No summary will be done with the combined subtypes. No statistical inferences will be made.

Percent change will be calculated as follows:

- If baseline value is 0, change from baseline \* 100
- Otherwise, change from baseline/baseline result \* 100

The number of CSMBs will be summarized by week including the changes from baseline. Since these quantities are not expected to follow a normal distribution, the median changes from baseline and median percent changes from baseline will be compared using the Mann-Whitney test.

The percentage of days each week with at least one stool with a consistency of 6 or 7 will be summarized for IBS-C and a consistency of 1 or 2 will be summarized for IBS-D using the Bristol Stool Chart.

The derived data will be listed by evaluable week.

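### SAP 10.2 leaves baseline stool frequency per day while SAP 10.1.1 puts the weekly value per week, so the IBS-C stool criterion, followed literally, passes a subject who stays at 2 CSBMs per week

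*SAP*

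**What the plan says.** SAP 10.2 lists stool frequency among the daily diary measures and gives one baseline rule for all of them: the value is "calculated by summing the daily result over the 7-day period and dividing by the number of days with an assessment". It then adds one rescaling step, for a different measure: "The Stool Consistency baseline proportions will be multiplied by 100 to convert to a percentage". No rescaling is given for stool frequency.

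SAP 10.1.1 also divides the on-treatment values by the number of days assessed in the week, and then rescales: "The stool frequency will be multiplied by 7 to convert to a stools per week figure". The IBS-C stool component compares the two: "Improvement is defined as an increase of 1 or more complete spontaneous bowel movements (CSBMs) per week compared with baseline".

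Protocol 7.1 shows which unit is meant: "Stool frequency will be defined as a sum of weekly CSBMs".

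**The concern.** The two sides of the IBS-C comparison are in different units. The baseline is stools per day and the treatment week is stools per week. Because SAP 10.2 repeats the factor of 100 for consistency and leaves out the factor of 7 for frequency, a programmer cannot safely assume that the conversion in SAP 10.1.1 carries over to baseline.

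This baseline decides half of the weekly response for the IBS-C cohort, and so feeds the primary endpoint. If stool frequency means weekly CSBMs, as Protocol 7.1 has it, the same baseline also enters SAP 11.3.2, where "the median changes from baseline and median percent changes from baseline will be compared using the Mann-Whitney test". A baseline that is too small by a factor of 7 makes subjects look improved when they are not.

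**Working it through.** The plan gives no worked figure for this step, so there is none to reproduce.

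**Inputs**
- Eligible IBS-C baselines: Protocol 5.1 requires that "Subject must have fewer than 3 CSBMs" occur in the 7-day period, so the baseline count c0 is 0, 1 or 2.
- Days assessed: SAP 10.2 treats a baseline with fewer than 4 of 7 days as missing. For treatment weeks, SAP 10.4 says "the weekly values will be considered missing if there are less than 4 days with data assessed within a week". So d0 (baseline days) and d (days in the week) each run from 4 to 7, giving 4 × 4 = 16 pairs.
- c is the number of CSBMs recorded in the treatment week.

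**Formulas**
- As written: 7c/d − c0/d0 ≥ 1.
- In the same units: 7c/d − 7c0/d0 ≥ 1.
- The first change exceeds the second by 6c0/d0, which is never negative. The literal rule can therefore add passes but never remove one, and it cannot affect a subject with c0 = 0.

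**Examples**

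| Baseline | Treatment week | Change as written | Change in same units |
|---|---|---|---|
| 2 in 7 days | 2 in 7 days | 2 − 0.286 = 1.714, pass | 2 − 2 = 0, fail |
| 1 in 7 days | 1 in 7 days | 1 − 0.143 = 0.857, fail | 1 − 1 = 0, fail |
| 1 in 7 days | 1 in 6 days | 1.167 − 0.143 = 1.024, pass | 1.167 − 1 = 0.167, fail |
| 1 in 6 days | 1 in 6 days | 1.167 − 0.167 = 1.00, pass | 1.167 − 1.167 = 0, fail |
| 2 in 7 days | 1 in 5 days | 1.4 − 0.286 = 1.114, pass | 1.4 − 2 = −0.60, fail |

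The last row is a fall in frequency that counts as improvement.

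**Full enumeration** (c0 = 0, 1, 2; d0 and d = 4 to 7; c = 0 to 7)
- The decision differs in 43 combinations: 0 at baseline 0, 15 at baseline 1 and 28 at baseline 2. All 43 are false passes.
- At baseline 1 a false pass is possible in 15 of the 16 day-count pairs (all but 7 and 7). At baseline 2 it is possible in all 16.
- With a complete 7-day baseline, 8 combinations remain: 3 at baseline 1 and 5 at baseline 2.
- With both weeks complete, one remains: baseline 2 and exactly 2 in the week.

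**Illustration of frequency** (assumptions, not from the documents: Poisson weekly counts, full diaries, baseline 2). The correct rule passes at 3 or more and the literal rule at 2 or more, so the extra passes equal P(X = 2). At a true mean of 2 per week this is 0.594 − 0.323 = 0.271. At means of 1, 3 and 4 it is 0.184, 0.224 and 0.147.

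**SAP 11.3.2 percent change.** For an unchanged subject with weekly baseline b > 0, the literal result is 100 × (b − b/7)/(b/7) = 600%; the correct value is 0%. A subject who truly rises from 0 to 1 per week gets 1 × 100 = 100% under that section's zero-baseline rule, and so ranks below the unchanged subject.

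**The case against.** The best reply is that the literal reading contradicts the plan's own intent. The criterion in SAP 10.1.1 is worded per week, Protocol 7.1 defines stool frequency as a weekly sum, and the multiply-by-7 sentence in SAP 10.1.1 is not expressly limited to post-baseline values. SAP section 6 requires double independent programming of tables and datasets. The documents do not show how the baseline was programmed. All of this stands, and it makes the defect an omitted conversion line rather than proof of a wrong analysis. Double programming is only a partial safeguard, because both programmers work from the same text.

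Four limits on the size also stand.
- The day-count pairs and the 43 combinations are counts of possibilities, not frequencies. Most of them need an incomplete baseline diary, and subjects are asked to complete all 7 days.
- Both arms use the same derivation. With no treatment effect they have the same false-pass probability, so the error does not inflate type I error. What suffers is the meaning of the endpoint, and possibly the response rates and power.
- For percent change among subjects with non-zero baselines, the literal value 7w/b − 1 (w is the weekly value, as a ratio) rises with the correct value w/b − 1. Their ranks do not change. Only their ranking against zero-baseline subjects moves. Ranks of absolute change can still move.
- SAP 11.3.2 treats weekly stool frequency and number of CSBMs in separate paragraphs. The effect on the Mann-Whitney test depends on their being the same variable. Protocol 7.1 makes that the natural reading, but SAP 11.3.2 does not say so.

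**Conclusion.** The concern holds. SAP 10.2 states a complete baseline rule, and that rule combined with SAP 10.1.1 gives a wrong stool decision for some IBS-C subjects. For subjects who meet the entry criterion and keep full diaries, the error is confined to those with 2 CSBMs at baseline who have exactly 2 in the week. Incomplete diaries extend it to baseline 1 and to some weeks in which frequency fell. It always favours improvement.

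The net effect on overall response, or on the treatment difference, cannot be computed. The documents do not give the share of subjects at baseline 1 or 2, diary completeness, or how often pain and stool response coincide. The pain decrease of at least 30% is still needed in the same week, and over enough weeks. IBS-D is untouched. In the IBS-C logistic model the missing factor would only rescale the coefficient of the baseline covariate. It should be fixed because it sits in the definition of a primary endpoint and costs almost nothing to correct.

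**What to change.** Add one sentence to SAP 10.2 stating that baseline stool frequency (CSBMs) is also multiplied by 7, so that it is expressed per week like the on-treatment value. Confirm that the analysis datasets hold it in that unit, and state in SAP 11.3.2 whether its CSBM analysis uses the same baseline. This needs no extra data and no change to the design.

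Three separate small points can go into the same edit.
- SAP 7.2 gives Week 3 as days 15–28. That is 28 − 15 + 1 = 14 days and overlaps Week 4; 7-day intervals give days 15–21.
- SAP 10.1.2.2 describes the consistency measure in terms of an increase in stools. It should match SAP 10.1.1: the share of days with a Type 6 or 7 stool, and its change from baseline.
- As a query only, confirm that SAP 11.3.2 intends Types 6/7 for IBS-C and Types 1/2 for IBS-D. The protocol synopsis names stool consistency as the Cohort C secondary endpoint, so a Type 1/2 summary for IBS-C could be considered. It would be one more table and is optional.

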### 10.3 Adjustments for Covariates

The primary analysis (proportion of overall responders) will not be stratified or adjusted for any covariates.

The proportion of subjects who are overall responders will be analyzed with both subtypes combined in a stratified analysis using the Cochran-Mantel-Haenszel (CMH) statistic.

The proportion of subjects who are overall responders will be further analyzed using separate logistic regression models for each subtype including terms for treatment group, region (US or UK and Ireland), the baseline week average of Abdominal Pain Intensity, and the subtype-specific baseline value. For the IBS-D model, the baseline covariate will be the proportion (as %) of days during the 7 consecutive days prior to baseline used for eligibility, with at least one bowel movement of Type 6 or 7. For the IBS-C model, the baseline covariate will be the baseline week average stool frequency.

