10.5.2 Secondary Efficacy Analysis

Primary Endpoint:

[figure not shown]
Secondary Analyses of the Primary Endpoint will include the use of baseline characteristics as covariates and analyses using the Efficacy Evaluable Analysis Set.

Secondary Efficacy Endpoints:

Secondary efficacy endpoints will be compared between the two treatment groups within each Cohort using Pearson's test with Yates's correction, the Mann Whitney test or other standard statistical tests as appropriate.

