## 5. DETERMINATION OF SAMPLE SIZE

Within each cohort (IBS-C or IBS-D) 125 subjects per treatment group (Blautix™ or Placebo) will provide at least 80% power to demonstrate a statistically significant difference in response rate between treatment groups at a one-sided alpha of 10% using Pearson's test with Yates' correction when the true response rate in the Placebo group is 40% and the true response rate in the Blautix™ group is 55%.

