# 11. METHODS OF EFFICACY ANALYSIS

## 11.1 Primary Efficacy Analyses

For the primary analysis of the overall response rate, as defined in [Section 10.1.1](#), the following one-sided hypotheses will be tested with a significance level  $\alpha=0.10$ :

$$H_0: \pi_T - \pi_P \leq 0 \leftrightarrow H_1: \pi_T - \pi_P > 0$$

where  $\pi_T$  and  $\pi_P$  are the proportions of overall responders under active treatment and placebo after 8 weeks of treatment, respectively. The hypotheses will be tested using the FAS using Pearson's chi-square test with Yates' continuity correction. As this is a one-sided chi-square test, the p-value from

the test will be divided by two if the difference is in favor of the Blautix arm ( $\pi_T > \pi_P$ ) and divided by two then subtracted from 1 if the difference is in favor of the placebo arm ( $\pi_T \leq \pi_P$ ).

The test will be applied separately to each IBS subtype.

Summary statistics will show the frequency of overall responders in each subtype and treatment group, the percentage of responders in each treatment group within subtype, the treatment difference in percentages within each subtype (active – placebo), and 80% Wald (asymptotic) confidence intervals, with continuity correction, for the differences in percentages.

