## 11.2 Additional Analyses of the Primary Efficacy Endpoint

As a sensitivity analysis, the primary efficacy analysis of the overall response rate will be repeated for the Efficacy Evaluable Set.

The remaining additional summaries and analyses will be done using the FAS.

The overall response rate will be analyzed with the IBS subtypes combined. A CMH test stratified by subtype will be used to test for an overall difference between the treatment groups across the subtype strata. To correspond with the primary analysis, the significance level will be two-sided 0.20 and an 80% CI for the treatment difference will be provided.

The primary efficacy endpoint (overall response) will be summarized and analyzed using the same method as the primary analysis by subgroups formed by sex and by region (US, UK and Ireland). The CMH analysis of overall response stratified by subtype will also be presented by sex and by region.

The frequencies and percentages of responders and non-responders by week during the treatment period will be summarized by IBS subtype and treatment group. A summary for the subtypes combined will be included. No CIs or inferences will be given.

The overall response rate will be further analyzed using a logistic regression model for each subtype. The models will include treatment and region (US, UK and Ireland) as factors and the baseline week average of Abdominal Pain Intensity and the subtype-specific baseline value as covariates. For the IBS-D model, the baseline covariate will be the proportion (as %) of days during the consecutive week prior to baseline, used for assessment of eligibility assessment, with at least one bowel movement Type 6 or 7. For the IBS-C model, the baseline covariate will be the average stool frequency in the week prior to baseline as noted for IBS-D. Model based odds ratios will be reported with 95% CIs.

The weekly average Abdominal Pain Intensities, the Abdominal Pain Intensity differences (baseline – weekly average, such that positive differences indicate improvement), and the percent differences [ $100 * (\text{baseline} - \text{weekly average}) / \text{baseline}$ ] will be summarized by IBS subtype (including combined), treatment group, and week across the treatment period and follow-up.

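### The primary responder test is valid and meets its stated power, but leaving out baseline values that the plan already models, and applying a continuity correction, gives up a few points of power

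*SAP*

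**What the plan says.** SAP 10.3: "The primary analysis (proportion of overall responders) will not be stratified or adjusted for any covariates". SAP 11.1 sets the test: "The hypotheses will be tested using the FAS using Pearson's chi-square test with Yates' continuity correction", one-sided at 0.10 and separately in each subtype. Protocol 10.5.1 names the same test and makes every other analysis of the primary endpoint secondary.

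The sample size rests on that test, "at a one-sided alpha of 10% using Pearson's test with Yates' correction". SAP 5 says that 125 subjects per arm in each cohort "will provide at least 80% power to demonstrate a statistically significant difference in response rate between treatment groups", at true rates of 40% and 55%.

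Covariates are planned, but as support. Protocol 10.5.2: "Secondary Analyses of the Primary Endpoint will include the use of baseline characteristics as covariates and analyses using the Efficacy Evaluable Analysis Set". SAP 11.2: "The overall response rate will be further analyzed using a logistic regression model for each subtype". The terms are treatment, region, baseline pain and the subtype-specific stool baseline. The output is odds ratios with 95% CIs. In the same section the stratified CMH analysis is deliberately set to two-sided 0.20 with an 80% CI, to match the primary analysis.

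**The concern.** Response is judged against each subject's own baseline (SAP 10.1.1), and the baseline diary is needed for eligibility (protocol 5.1). Baseline pain and stool values are therefore available at no extra cost and are plausible predictors of response. Protocol 5.3.1 describes 1:1 allocation within cohort and names no other stratification factor, so nothing described in the design limits chance imbalance in them.

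A pre-specified adjustment for prognostic baselines usually raises power without inflating the error rate. Here the adjusting model is already written, but the decision rests on a test that uses neither the covariates nor the full 10% error rate that the sponsor chose. At stake is a modest rise in the chance of detecting a real effect in each cohort. The documents give no reason for leaving the primary test unadjusted.

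**Working it through.** **Inputs.** From SAP 5 and protocol 10.2: n = 125 per arm, placebo rate 0.40, active rate 0.55, one-sided alpha 0.10 (z = 1.2816), Pearson test with Yates correction. The prognostic strength of the baselines is not in the documents, so it is assumed and varied.

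**1. Reproduce the stated power.**

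- Pooled rate: (0.40 + 0.55)/2 = 0.475.
- Null SE: √(0.475 × 0.525 × 2/125) = 0.0632.
- Alternative SE: √((0.40 × 0.60 + 0.55 × 0.45)/125) = 0.0624.
- The Yates correction takes 1/n = 0.008 off the difference.
- Approximate power: Φ[(0.15 − 0.008 − 1.2816 × 0.0632)/0.0624] = Φ(0.978) = 83.6%.
- Exact power, summing the binomial probabilities of all pairs of counts that reject: **82.5%**.

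The stated 80% or more holds. The continuity-corrected sample-size formula needs 112 per arm.

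**2. Isolate the continuity correction.** The same exact sum without it gives 85.6%, so the correction costs 85.6 − 82.5 = 3.1 points. Exact type I error:

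| Common response rate | With Yates | Without |
|---|---|---|
| 40% | 8.2% | 10.4% |
| 47.5% | 7.3% | 9.3% |

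**3. Add covariates by simulation.** Response follows a logistic model with two independent standard normal covariates, with intercepts set so that the marginal rates are 40% and 55%. The adjusted test is the one-sided 0.10 Wald test for treatment.

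With 4,000 trials per scenario, the last column compares against the exact uncorrected power of 85.6%:

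| Log-odds per SD | Yates | Adjusted | Covariate gain |
|---|---|---|---|
| 0.3, 0.3 | 82.4% | 87.4% | 1.8 |
| 0.5, 0.3 | 82.7% | 88.4% | 2.8 |
| 0.6, 0.6 | 83.0% | 90.1% | 4.5 |

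A second set has 6,000 trials per scenario, a non-prognostic region term in the model, and equal log-odds for the two covariates. R² is the share of response variance explained. The gain is taken against the uncorrected unadjusted test in the same trials:

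| Log-odds per SD | R² | Yates | Uncorrected | Adjusted | Covariate gain |
|---|---|---|---|---|---|
| 0 | 0 | 82.5% | 85.5% | 86.2% | 0.7 |
| 0.18 | 0.015 | 82.7% | 85.9% | 87.1% | 1.2 |
| 0.35 | 0.05 | 81.6% | 84.9% | 87.4% | 2.4 |
| 0.53 | 0.11 | 82.7% | 86.1% | 89.6% | 3.5 |

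The Monte Carlo SE is about 0.5 point. The 0.7 at R² = 0 cannot be a precision gain, since those covariates carry no information. Stronger prediction would give more (adjusted power 90.6% at R² 0.17 and 93.4% at 0.29), but nothing in the documents supports assuming it. A standardised risk difference has the same power to within about 0.1 point.

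**4. Error rate of the adjusted test.** Under the null at a 40% common rate, the adjusted test rejects in 9.7% to 10.4% of trials. The Monte Carlo SE is √(0.10 × 0.90/6000) = 0.4 point, so there is no material inflation.

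**The case against.** A reader might infer that the plan is underpowered, or that the unadjusted test buys nothing. Neither reading is supported.

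- **The design is coherent.** Sample size and primary analysis use the same test, and it meets its stated power. A randomised unadjusted comparison is valid, and covariate adjustment is pre-specified as a secondary analysis, so chance imbalance will be examined. This stands in full.
- **The covariate gain is an assumption.** A response defined as a percentage fall from baseline may already remove much of the dependence on baseline. Eligibility also narrows the range: pain above 3.0, and fewer than 3 CSBMs a week or Type 6/7 stools on at least four days. Weak prediction is plausible, and the gain would then be about 1 point or less. This stands.
- **Much of the apparent gain is the continuity correction.** At log-odds of 0.3, about 3 of the 5 points come from dropping it. The lower type I error of the planned test is also largely the correction. This stands, and the two effects are separated above.
- **The simple test has merits.** It needs no model and gives a difference in response rates directly. It can also keep subjects without a valid baseline (fewer than 4 of 7 days, SAP 10.2) as non-responders under protocol 10.7, whereas a logistic model drops them unless a rule is added. This stands in part. SAP 8 already allows response analyses on the subset with valid baselines, and a standardised risk difference is also a difference in response rates.

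**Conclusion.** The plan contains no error here. The planned test is valid and has exact power of 82.5%. A better use of data already collected would raise that to about 86-87% if the baselines predict weakly, and to about 87-90% at log-odds of 0.3 to 0.6 per SD. About 3 points belong to the continuity correction, and under 1 to about 4.5 to the covariates.

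The 82.5% and the type I error of 7.3-8.2% are exact under the plan's own inputs. The covariate figures rest on an assumed prognostic strength, two independent normal covariates and no missing baselines. The change is worth making if it can still be made blind. It is not needed for the trial to be interpretable.

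**What to change.** Before any unblinded result is produced:

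- Make the SAP 11.2 covariate model the primary analysis in each cohort. Report a standardised (marginal) risk difference with an 80% CI and a one-sided 0.10 test. Keep the Yates-corrected test as supportive.
- State one coding of region. SAP 10.3 reads as two levels (US; UK with Ireland), while the list in SAP 11.2 could be two or three.
- State a missing-baseline rule that keeps every FAS subject, for example simple imputation of the baseline covariate with the subject counted as a non-responder, and reconcile it with the valid-baseline subset in SAP 8.
- Change protocol 10.5.1 and SAP 10.3, 11.1 and 13 to match.

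**Timing.** The SAP 10.5 interim sends unblinded efficacy tables, with arms masked, to a sponsor executive. They cover the primary analysis and the additional analyses of the same endpoint, which include this model. A switch after that look would be a choice between results already seen.

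**Cost.** No new data. The primary estimate becomes model-based. The protocol text must be amended, because protocol 10.4 exempts only minor changes and replacing the primary test is arguably not minor.

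**If the primary cannot change,** report the adjusted model as a standardised risk difference with an 80% CI and a one-sided 0.10 test, so that it corresponds with the primary analysis as the CMH analysis already does.
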